9.3 Immunogenicity

Anti-drug (UCB6114) antibody status and classification, changes from Baseline in titer over time (Cycles 1, 2 and even cycles thereafter) and the incidence of treatment-emergent ADA positivity are exploratory immunogenicity endpoints in Part B of this study. Potential relationships between ADA and PK, PD, antitumor activity and safety will also be explored but this will be reported separately outside of the CSR.

Serum samples will be collected from all study participants for the measurement of ADA and the evaluation of immunogenicity according to the Schedule of Activities in the protocol.

All listings of ADA will be presented for the SS and summaries of the ADA data will be presented by treatment group for the ADAS.

Anti-drug (UCB6114) antibodies will be measured using a three-tiered assay approach: Screening assay, confirmatory assay and titration assay.

Samples will first be evaluated in the Screening assay using a false positivity rate of 5% (reported as ‘negative screen’ or ‘positive screen’), followed by analysis of screened positive samples in the confirmatory assay (which is a drug depletion assay) to confirm the positivity of the samples (reported as ‘negative immunodepletion’ or ‘positive immunodepletion’). Samples that are confirmed as positive in the confirmatory assay will be evaluated in a titration assay to assess the ADA level and this will be reported as titer (reciprocal dilution factor including minimum required dilution).

Anti-drug (UCB6114) antibody sample status will be determined as follows from the pre-treatment sample taken on Day 1 of Cycle 1 (Baseline) and all post-treatment (post-Baseline) samples.

- Sample values that are either ‘negative screen’ or ‘positive screen’ and ‘negative immunodepletion’ will be defined as **ADA negative**
- Sample values that are ‘positive screen’ and ‘positive immunodepletion’ will be defined as **ADA positive**

Anti-drug (UCB6114) antibody sample status will be listed for each participant at each visit by treatment group. This listing will include sampling dates and times, the Screening assay result, the confirmatory assay result and the derived ADA sample status. In addition, the titer from the

titration assay (if applicable) will be listed together with the change from Baseline in titer. The number and percentage of participants with a positive or negative sample at each visit will be summarized by treatment group. Percentages will be calculated based on the number of participants with a non-missing/sufficient sample at the visit.

Based on the ADA status of the samples, study participants will be categorized according to the following 6 ADA classifications in [Table 9-2](#):

Table 9-2: ADA Classifications

Classification	Classification Label	Definition
1	Pre-ADA negative – treatment induced ADA negative	Includes participants who have an ADA negative status at Baseline, or missing/insufficient Baseline sample, and an ADA negative status at all sampling timepoints post-Baseline (including SFU). Participants with missing post-Baseline samples are included as long as the missing samples do not result in an unmonitored period greater than 16 weeks.
2	Pre-ADA negative – treatment induced ADA positive	Includes participants who have an ADA negative status at Baseline, or missing/insufficient Baseline sample, and an ADA positive status at any sampling timepoint post-Baseline (including SFU).
3	Pre-ADA positive – treatment reduced ADA	Includes participants who have an ADA positive status at Baseline and an ADA negative status at all sampling timepoints post-Baseline (including SFU)
4	Pre-ADA positive – treatment unaffected ADA	Includes participants who have an ADA positive status at Baseline and an ADA positive status at any sampling timepoint post-Baseline (including SFU) with titer values of the same magnitude as Baseline (≤ 1.80 fold difference from the Baseline value) or with decreased titer values compared to Baseline (> 1.80 fold decrease from the Baseline value).
5	Pre-ADA positive – treatment boosted ADA positive	Includes participants who have an ADA positive status at Baseline and an ADA positive status at any sampling timepoint post-Baseline (including SFU) with increased titer values compared to Baseline (> 1.80 fold increase from the Baseline value).
6	Inconclusive	Includes participants who do not satisfy the criteria for classifications 1-5.

ADA=anti-drug (UCB6114) antibody; SFU=Safety Follow-up.

Note: The terminology ‘treatment unaffected’ is ambiguous as the criteria refers to ADA responses that are not increased upon dosing compared to Baseline level whereas titers may reduce.

The number and percentage of participants in each of the 6 ADA classifications defined above in [Table 9-2](#) will be presented by treatment group. Also, in this tabulation, ADA incidence and prevalence (as defined above) will be summarized.

The first occurrence of treatment-emergent ADA positivity (based on the criteria above) will be summarized using frequency counts and percentages at each post-Baseline visit by treatment group. This tabulation will include a count of the number of participants at each post-Baseline visit who fulfill at least one of the above defined criteria for treatment-emergent ADA positivity; participants will be counted in the numerator based on the earliest visit at which one of these criteria is fulfilled. At other visits, participants will be counted in the denominator (assuming an assessment of treatment-emergent positivity is available) and this will be used in the percentage calculations.

Individual study participant ADA titer profiles over actual time will be presented graphically on the linear and the semi-logarithmic scale. The linear scale plots will be repeated for the subset of participants who achieve treatment-emergent ADA positivity during Part B.

Mean (\pm standard deviation) C_{min} will be plotted by ADA sample status over nominal (scheduled) time with treatment groups overlaid on the same plot. On this plot, mean C_{min} at Cycle 1 Day 15 will be the mean of the derived C_{min} following the first dose of UCB6114 (as described in [Section 9.1.2](#)) and, thereafter from Cycle 2 Day 1, mean C_{min} will be the mean of the predose concentrations at the subsequent dosing visits.

10. EFFICACY ANALYSES

10.1 Antitumor activity

The analysis of antitumor activity is exploratory in Part B of this study.

10.1.1 Definitions of the antitumor activity endpoints

The following endpoints are defined based on RECIST (Version 1.1) which standardizes solid tumor measurements and provides guidelines for the objective assessment of changes in tumor size during anti-cancer treatment.

Appendix 9 (Section 11.9) of the protocol contains the RECIST 1.1 guidelines to be used in this study, adapted from Eisenhauer (2009), and includes the definitions of target and non-target lesions, the definitions of target and non-target lesion responses at each tumor assessment, the criteria for determining overall response at each tumor assessment based on target lesion response, non-target lesion response and the presence/absence of new lesions, and a participant's best overall response (BOR). Further details on the rules to apply in the derivation of BOR are included in the Derivation of Efficacy Endpoints document which has been developed to support this SAP.

At each post-Baseline tumor assessment, the investigator will record responses for target lesions and non-target lesions, whether or not there has been an appearance of any new lesions, and the participant's overall response based on their target lesion response, non-target lesion response and the presence/absence of new lesions. Note that target lesion response and non-target lesion response assessments will be based on the changes in the pre-existing lesions at Baseline and the appearance of new lesions will only factor in the determination of an overall response of PD at that tumor assessment visit (i.e. per Tables A and B in Section 11.9.2 of Appendix 9 of the protocol).

Objective response rate (ORR) is defined as the percentage of participants with a BOR of complete response (CR) or partial response (PR) during Part B.

Disease Control Rate (DCR) is defined as the percentage of participants with a BOR of CR, PR, or stable disease (SD) during Part B.

Best overall response (BOR) is defined for each study participant as the best overall tumor response from each tumor assessment performed every 8 weeks from Day 1 of Cycle 1 (\pm 7 days) according to the RECIST criteria for changes in target and non-target lesions and the appearance of new lesions. Best overall response is determined from the start of study treatment (first dose of UCB6114) until documented objective disease progression or the date of subsequent anti-cancer therapy (systemic therapy, surgery or radiotherapy for cancer), whichever

occurs first. If anti-cancer therapy is started on the same day as a tumor assessment, then the overall response from that assessment will be used in the derivation of BOR. If a participant does not have objective disease progression or does not start a subsequent anti-cancer therapy, then all tumor assessments up to the SFU visit will be included in the derivation of BOR. For a BOR of SD, a participant's tumor measurements must have met the SD criteria at least once after the start of study treatment at a minimum interval of no less than 49 days.

For this study, BOR determination requires confirmation of CR or PR responses at a subsequent assessment ≥ 4 weeks (28 days) after the criteria for CR or PR responses are first met, however, an unconfirmed BOR will also be derived for each participant for the purpose of reporting (as described below in [Section 10.1.2](#)). Table C in Appendix 11.9 of the protocol and Table 1 and subsequent text in the Derivation of Efficacy Endpoints document provides the derivation of BOR when confirmation of CR and PR responses are required. The definition of an unconfirmed BOR is also included in this document. Although the derivation of unconfirmed BOR does not include the requirement for a CR or PR response to be confirmed ≥ 4 weeks (28 days) after the initial response, a participant's CR or PR response may, in fact, be confirmed at a subsequent assessment ≥ 4 weeks (28 days) after the criteria for the CR or PR response are first met. Unconfirmed BOR will be referred to as BOR (confirmed or unconfirmed) throughout the rest of this document.

Confirmed BOR and BOR (confirmed or unconfirmed) will be derived programmatically based on the overall tumor assessment data recorded on the eCRF by the investigator.

Duration of response (DOR) will be calculated for participants with a BOR of confirmed CR or PR as the time in days from the start date of the confirmed CR or PR (e.g. the date of the first overall response of CR or PR, which is at least 4 weeks before a second overall response of CR or PR) to the first date that recurrent or progressive disease is objectively documented (i.e. according to the RECIST guidelines). This will be referred to as the duration of confirmed response and the following calculation will be performed:

$$\begin{aligned} \text{Duration of Confirmed Response} \\ = & (\text{Date of First Objective Disease Progression} \\ & - \text{Start Date of Confirmed CR or PR Response}) + 1 \end{aligned}$$

Duration of response will also be calculated for participants with a BOR of CR or PR which is either confirmed or unconfirmed [DOR (confirmed or unconfirmed)] as the time in days from the start date of the CR or PR to the date of the first documented objective disease progression (i.e. according to the RECIST guidelines). The following calculation will be performed:

$$\begin{aligned} \text{DOR (Confirmed or Unconfirmed)} \\ = & (\text{Date of First Objective Disease Progression} \\ & - \text{Start Date of CR or PR Response}) + 1 \end{aligned}$$

For the purpose of a sensitivity analysis of both duration of confirmed response and DOR (confirmed or unconfirmed), the above calculations will take into consideration the occurrence of both objective disease progression (per RECIST 1.1) and clinical disease progression (as described in Appendix 11.9 of the protocol and as determined by the investigator and recorded as a reason for study treatment discontinuation on the eCRF), whichever occurs first. If clinical disease progression occurs on the same date that a participant's objective disease progression is

determined, then the participant will be included in the sensitivity analyses as having objective disease progression.

The following calculations will therefore be performed for the sensitivity analyses:

Duration of Confirmed Response

$$= (\text{Date of First Objective or Clinical Disease Progression} - \text{Start Date of Confirmed CR or PR Response}) + 1$$

DOR (Confirmed or Unconfirmed)

$$= (\text{Date of First Objective or Clinical Disease Progression} - \text{Start Date of CR or PR Response}) + 1$$

For participants who die without objective disease progression, DOR will be censored on the date of death, regardless of cause. For a participant who discontinues early from Part B of the study with no objective disease progression, DOR will be censored on the date of their last available (scheduled or unscheduled) tumor assessment at which a lack of objective disease progression was determined. Participants who discontinue study treatment but who do not have documented objective disease progression (i.e. according to the RECIST guidelines), DOR will be censored at the date of their last available (scheduled or unscheduled) tumor assessment at which a lack of objective disease progression was determined. Such participants might include those that are ongoing in Part B at the time of any defined data cut-off. Likewise, participants who have not discontinued early and do not have disease progression after a confirmed or unconfirmed response, DOR will be censored at the date of their last available (scheduled or unscheduled) tumor assessment.

In the sensitivity analyses of duration of confirmed response and duration of unconfirmed response, the same censoring rules will apply except that the date of last contact will be used for the censoring of participants who discontinue early from Part B or complete Part B without objective disease progression, clinical disease progression or death.

Date of last contact will be the latest of the dates of premature study termination and of last contact recorded on Study Termination eCRF page, the date of death, the date of last dose of study treatment, the dates of all visits, AE start and end dates (with partial dates imputed as earliest possible) and the date of contact recorded on the Survival Safety Follow-up and Survival Final Follow-up eCRF forms.

Further details on the rules to apply in the derivation of DOR are included in the Derivation of Efficacy Endpoints document which has been developed to support this SAP.

Progression-free survival (PFS) will be calculated as the time in days from the first dose of UCB6114 to the date of the first documented objective disease progression (i.e. according to the RECIST guidelines), or death due to any cause, whichever occurs first. The following calculation will be performed:

$$PFS = \left(\text{Date of Objective Progressive Disease} - \text{Date of First Dose of UCB6114} \right) + 1$$

Participants who die due to any cause without a documented objective disease progression will be considered to have progressed on the date of their death. Participants who do not have any post-Baseline tumor assessments will be censored on the date of their first dose of UCB6114. Participants who discontinue early from Part B or discontinue study treatment without

documented objective disease progression or death, will be censored on the date of their last available (scheduled or unscheduled) tumor assessment at which a lack of objective disease progression was determined. Participants who start anti-cancer therapy during Part B without a prior documented objective disease progression will be censored on the date of their last available (scheduled or unscheduled) tumor assessment prior to the initiation of the subsequent anti-cancer therapy. If anti-cancer therapy starts on the same date as the participant's tumor assessment and determination of objective disease progression, or the participant's death (due to any cause), then the participant will not be censored and the participant will be included as having an uncensored event on this date. This censoring rule will also be applied to participants who are ongoing at any data cut-off for an analysis of Part B data who have no documented objective disease progression. The use of anti-cancer therapy during Part B will be identified via ongoing medical review of the concomitant medications together with the start dates of further anti-cancer therapy information recorded on the survival follow-up pages of the eCRF.

As a sensitivity analysis, PFS will also be calculated as the time in days from the first dose of UCB6114 to the date of the first documented objective disease progression (per RECIST 1.1), the date of clinical disease progression, as determined by the investigator, or the date of death due to any cause, whichever occurs first. Last contact date will be used for the censoring of participants still alive with no reported disease progression (objective or clinical). The same rules described above for the censoring of participants who start anti-cancer therapy will be applied in this sensitivity analysis.

Further details on the rules to apply in the derivation of PFS are included in the Derivation of Efficacy Endpoints document which has been developed to support this SAP.

Overall survival (OS) will be calculated as the time in days from the date of first dose of UCB6114 to the date of death from any cause. Participants will be followed up to ascertain their survival status at the SFU visit (within 30 days after their last dose of UCB6114) and at the Final Visit (3 months after their last dose of UCB6114); they will not be followed up beyond this timepoint.

The following calculation will be performed:

$$OS = (Date of Death - Date of First Dose of UCB6114) + 1$$

OS will be censored on the date of their last contact for participants who discontinue early from Part B of the study or who discontinue study treatment due to disease progression but continue in the study, and are not known to have died.

Further details on the rules to apply in the derivation of OS are included in the Derivation of Efficacy Endpoints document which has been developed to support this SAP.

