Participants who die due to any cause without a documented objective disease progression will be considered to have progressed on the date of their death. Participants who do not have any post-Baseline tumor assessments will be censored on the date of their first dose of study treatment. Participants who discontinue early from Part C or discontinue study treatment without

documented objective disease progression or death, will be censored on the date of their last available (scheduled or unscheduled) tumor assessment at which a lack of objective disease progression was determined. Participants who start anti-cancer therapy during Part C without a prior documented objective disease progression will be censored on the date of their last available (scheduled or unscheduled) tumor assessment prior to the initiation of the subsequent anti-cancer therapy. If anti-cancer therapy starts on the same date as the participant's tumor assessment and determination of objective disease progression, or the participant's death (due to any cause), then the participant will not be censored and the participant will be included as having an uncensored event on this date. This censoring rule will also be applied to participants who are ongoing at any data cut-off for an analysis of Part C data who have no documented objective disease progression. The use of anti-cancer therapy during Part C will be identified via ongoing medical review of the concomitant medications together with the start dates of further anti-cancer therapy information recorded on the survival follow-up pages of the eCRF.

As a sensitivity analysis, PFS will also be calculated as the time in days from the first dose of study treatment to the date of the first documented objective disease progression (per RECIST 1.1), the date of clinical disease progression, as determined by the investigator, or the date of death due to any cause, whichever occurs first. Last contact date will be used for the censoring of participants still alive with no reported disease progression (objective or clinical). The same rules described above for the censoring of participants who start anti-cancer therapy will be applied in this sensitivity analysis.

Further details on the rules to apply in the derivation of PFS are included in the Derivation of Efficacy Endpoints document which has been developed to support this SAP.

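### Duration of response censors responders at death in every planned analysis, so the Kaplan-Meier estimate overstates time in response; the PFS no-scan rule needs a qualifier for deaths

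*SAP*

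**What the plan says.** All rules below are in SAP section 10.1.1, once for Part B and once for Part C.

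- **DOR event.** DOR runs from the start of the response "to the first date that recurrent or progressive disease is objectively documented". The formulas for confirmed response and for confirmed or unconfirmed response contain a progression date and no death date.
- **DOR, death.** "For participants who die without objective disease progression, DOR will be censored on the date of death, regardless of cause".
- **DOR, sensitivity analysis.** Clinical progression is added as an event. For censoring, "the same censoring rules will apply except that the date of last contact will be used for the censoring of participants who discontinue early" or complete the Part without progression or death. That exception keeps dead participants out of the last-contact rule but does not make their death an event, and the sensitivity formulas have no death term.
- **PFS event.** Objective progression "or death due to any cause, whichever occurs first". Participants who die "without a documented objective disease progression will be considered to have progressed on the date of their death".
- **PFS, no scan.** Part B: "Participants who do not have any post-Baseline tumor assessments will be censored on the date of their first dose of UCB6114". Part C: "Participants who do not have any post-Baseline tumor assessments will be censored on the date of their first dose of study treatment".

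Section 10.1.2 summarises DOR and PFS by Kaplan-Meier, with quartiles and rates at 3, 6 and 9 months, where the data allow.

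**The concern.** Kaplan-Meier is valid only if a censored participant has the same future risk as those still under observation. A responder with advanced cancer who has died has no further time in response, so death is not non-informative censoring. The estimate answers how long responses would last if nobody died, and it will be read as how long responses lasted.

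Two features of the SAP sharpen this. First, the same death without progression is a failure in PFS and a censored observation in DOR, and no reason is given. Second, in the main DOR analysis a living participant without progression is censored at the last tumor assessment, while one who died is carried past the last scan to the date of death. The death rule therefore credits extra progression-free follow-up to the participants who did worst.

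The stakes are moderate. Antitumor activity is exploratory, but section 2.3 lists available antitumor activity among the information behind the recommended Phase 2 dose in each Part. Section 2.4 expects 3 to 9 participants per dose level, and responders are only some of these, so one or two deaths can move a DOR estimate.

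**Working it through.** The SAP states no expected DOR, PFS, event count or share of deaths, so there is no planned figure to reproduce. The direction follows from the rules. The sizes are illustrations under stated assumptions.

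**1. Direction.** The follow-up times, and hence the risk sets, are the same whether a death is coded as censored or as an event. Coding it as an event only adds a factor below 1 to the Kaplan-Meier product at the time of death. The planned curve therefore lies at or above the curve that counts deaths.

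**2. Size under constant hazards (assumed).** Let p be the hazard of progression, d the hazard of death without progression, and f = d/(p+d) the share of first events that are deaths.

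- Median with death as an event: ln 2/(p+d)
- Median estimated with death censored: ln 2/p
- Ratio: (p+d)/p = 1/(1-f)

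If the true 6-month rate is 50%, the planned analysis shows 0.5^(1-f).

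| Assumed f | Median inflated by | True 50% rate at 6 months reads as |
|---|---|---|
| 10% | 1/0.90 = 1.11 | 53.6% |
| 20% | 1/0.80 = 1.25 | 57.4% |
| 25% | 1/0.75 = 1.33 | 59.5% |
| 30% | 1/0.70 = 1.43 | 61.6% |

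**3. Mechanism in a small group.** Take five invented responders: death at 90 days, progression at 120, death at 150, progression at 200, censored at 240.

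- As planned: S(120) = 3/4 = 0.75 and S(200) = 0.75 × 1/2 = 0.375. Median 200 days.
- Death as an event: S(90) = 4/5 = 0.8, S(120) = 0.8 × 3/4 = 0.6, S(150) = 0.6 × 2/3 = 0.4. Median 150 days.

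Here two of the four events are deaths (f = 50%), above the range in the table. The example shows how the rule works and does not predict a size.

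**4. PFS overlap.** The first scan window is Day 50 to 64 (section 10.1.2). A participant who dies before any scan meets two adjacent rules: the death rule (event on the date of death) and the no-scan rule (censored at first dose). Neither excludes the other and no precedence is stated. The next rule, on early discontinuation, does exclude deaths.

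- If the death rule governs, the overstatement is zero.
- If the no-scan rule governed, k deaths among N participants would leave the risk set on Day 1, and a later PFS rate, before other censoring, would be multiplied by N/(N-k). One death among 9 gives 9/8 = 1.125, so a displayed 50% would be 50% × 8/9 = 44.4% with the death counted. Three deaths among 27 give the same factor, 27/24 = 1.125.

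**The case against.** The best defence is that DOR here is defined as time to objectively documented progression, and censoring at death follows from that definition. PFS names death as an event and DOR does not, so the two endpoints simply differ. The sensitivity DOR also counts clinical progression, which captures a responder taken off treatment for clinical decline before dying. The endpoints are exploratory and descriptive. Individual DOR times, event and censoring counts, survival status and dates of death are all reported, so a reader can find the deaths behind censored values.

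Part of this stands. The definition is explicit, the sensitivity analysis recovers some deaths, and the consequence is limited. But the choice is not explained, no planned DOR analysis counts death, and listings do not correct the Kaplan-Meier medians and rates.

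A reader might also infer that PFS is biased upward because the plan censors at Day 1 everyone who dies before a scan. The documents do not support that. The PFS definition includes death from any cause, the sentence just before the no-scan rule makes any death without progression an event, and the sensitivity PFS limits last-contact censoring to participants still alive. The more natural reading is that death is an event and the no-scan rule covers the rest. The separate Derivation of Efficacy Endpoints document, which is not shown, may settle the precedence.

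**Conclusion.** The DOR point holds in both Parts and in both the main and sensitivity analyses. Censoring at death can only raise the estimated DOR, and it is inconsistent with how the SAP treats the same death in PFS. The size cannot be read from the SAP. The 11% and 33% inflation of the median rest on constant hazards and on assumed death shares of 10% and 25% of first events, and if no responder dies without progression the effect is nil.

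For PFS only a wording gap is established: two overlapping rules without stated precedence for a death before the first scan. Upward bias there is conditional on the no-scan rule being applied to deaths.

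The change should be made, but since the endpoints are exploratory it does not threaten the primary safety objective.

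**What to change.** In section 10.1.1 for Part B and Part C:

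1. Define DOR as the time from the start of response to objective progression or death from any cause, whichever is first, for both the confirmed and the confirmed-or-unconfirmed versions. In the sensitivity analysis, use objective progression, clinical progression or death.
2. Delete the sentence that censors DOR at death, add the date of death to the four DOR formulas, and state in the sensitivity paragraph that death is an event on its date.
3. In the PFS no-scan rule, add *and are not known to have died*, so that a death before the first scan is an event on the date of death.
4. Check the Derivation of Efficacy Endpoints document and align it where it differs.

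The cost is SAP wording and a change to the derivation code. Dates of death are already collected, so no new data are needed. The downside is a less favourable DOR. PFS changes only if the no-scan rule would otherwise have been applied to deaths.

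### The DOR censoring rules in both SAPs make no provision for subsequent anti-cancer therapy, although BOR and PFS do, so DOR can run on into the next treatment and can exceed PFS

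*SAP*

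**What the plan says.** All the rules are in Section 10.1.1 of each SAP.

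- **BOR** is determined "until documented objective disease progression or the date of subsequent anti-cancer therapy (systemic therapy, surgery or radiotherapy for cancer), whichever" comes first. A scan on the day the new therapy starts still counts.
- **PFS, main analysis.** Part B: "Participants who start anti-cancer therapy during Part B without a prior documented objective disease progression will be censored on the date of their last available" scan before the new therapy. Part C has the parallel rule: "Participants who start anti-cancer therapy during Part C without a prior documented objective disease progression will be censored" in the same way. If progression or death falls on the day the new therapy starts, it counts as an event.
- **PFS, sensitivity analysis** keeps this: "The same rules described above for the censoring of participants who start anti-cancer therapy will be applied in this sensitivity analysis".
- **DOR, main analysis** gives rules for death without progression (censored at death), early discontinuation from the part, stopping study treatment without progression, and continuing without progression. For a participant who stopped treatment, "DOR will be censored at the date of their last available (scheduled or unscheduled) tumor assessment at which a lack of objective disease progression" is recorded. New anti-cancer therapy is not mentioned.
- **DOR, sensitivity analysis** adds clinical progression as an event. Otherwise "the same censoring rules will apply except that the date of last contact will be used for the censoring of participants" who discontinue early, or complete the part, without progression or death. New therapy is again not mentioned.

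Section 4.3 of each SAP feeds all scheduled and unscheduled tumor assessments into BOR, DOR and PFS, with no cut-off for DOR.

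**The concern.** DOR, BOR and PFS are derived from the same scans in the same people. A response starts after the first dose, so under matching rules DOR cannot be longer than PFS. Here a responder who moves to surgery, radiotherapy or a new drug without objective progression leaves PFS at the last scan before that treatment but stays in DOR. Time on the next treatment can then be counted as duration of response to UCB6114 plus TFD/TPI or mFOLFOX6. The same progression can be an event for DOR while PFS is already censored. The planned Kaplan-Meier summaries, including DOR rates at 3, 6 and 9 months (Section 10.1.2), would mix the two.

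**Working it through.** The SAPs give no figure to reproduce, so the check sets the rules side by side and then follows one assumed responder.

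**Rules when new therapy starts before objective progression**

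| Endpoint | End of the clock |
|---|---|
| BOR | Start of new therapy |
| PFS, main | Last scan before new therapy |
| PFS, sensitivity | Last scan before new therapy |
| DOR, main | No rule for this case; later progression (event), last non-progression scan, or death (both censored) |
| DOR, sensitivity | No rule for this case; later objective or clinical progression (event), death, or last contact (both censored) |

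**Assumed dates** (first dose is Day 1)

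- Partial response on Day 57, the target day of the first scan in Section 10.1.2, confirmed on Day 113. No progression by then.
- Last UCB6114 dose on Day 113; new therapy on Day 120.
- SFU visit about 30 days after the last dose: 113 + 30 = Day 143.
- Final Visit about 3 months after the last dose: 113 + 91 = Day 204.

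**Formulas from Section 10.1.1:** DOR = (end date − response start) + 1; PFS = (end date − first dose) + 1.

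1. PFS, main and sensitivity, censored at Day 113: 113 − 1 + 1 = 113 days.
2. DOR if the PFS rule applied: 113 − 57 + 1 = 57 days, censored, whatever happens later.
3. DOR as written with a non-progression SFU scan on Day 143: 143 − 57 + 1 = 87 days, censored. The excess is 87 − 57 = 30 days, of which 143 − 120 = 23 fall after the new therapy started.
4. If that SFU scan shows progression, DOR is again 87 days but is now an event, while PFS stays censored at Day 113.
5. Sensitivity DOR with no progression and last contact at the Final Visit: 204 − 57 + 1 = 148 days, against a sensitivity PFS of 113.
6. When does DOR exceed PFS? (end − 57) + 1 > 113 requires an end date after Day 169. The SFU scan in step 3 does not reach this: DOR ends 30 days after PFS does, but 87 is still below 113. A death after Day 169 does, as does the last contact in step 5. The death case reads the PFS new-therapy rule as overriding the death rule, which the same-day exception implies.

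In the main analysis, extra time needs either a scan after the new therapy or a death. In the sensitivity analysis last contact is enough.

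**The case against.** **The rule may be elsewhere.** Section 10.1.1 refers to the Derivation of Efficacy Endpoints document for further DOR detail, and that document is not at hand. This stands as a limit: the gap is shown for the two SAPs only. It does not remove the point. The SAPs cite the same document for BOR and PFS and still print their new-therapy rules, and a cut at new therapy in that document would conflict with the printed DOR wording.

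**The impact is small.** This stands. Antitumor activity is exploratory, DOR is summarized only if the data allow, and there is no test. Each part enrolls up to 27 participants, with at most 9 evaluable per dose level. Those affected must respond and then switch without objective progression.

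**Stronger readings that the documents do not support**

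- *An excess of about 3 months.* A reader might put progression on the new therapy at Day 197 (197 − 57 + 1 = 141 days, 84 more than 57), or take 148 days from step 5 (91 more). The first needs an objective assessment after SFU. The SAPs describe disease assessment that late only as a listed item with survival status, and do not say that it feeds DOR. The second is largely the intended last-contact censoring: the same responder without new therapy would also have 148 days, but with a sensitivity PFS of 204. Responders who stop for clinical progression have an event at that point in the sensitivity analysis.
- *A distorted recommended Phase 2 dose.* Section 2.3 bases it on all the information, including available antitumor activity, but nothing ties it to DOR.
- *PFS missing cancer surgery or radiotherapy because concomitant procedures are not a named source.* Section 6.5 says only that such procedures are listed, not that cancer treatment is recorded there. The survival pages, a named source, collect further antitumor treatment and its type.

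**Conclusion.** The point holds as an inconsistency within Section 10.1.1 of both SAPs. Followed as written, the DOR rules can count time on subsequent therapy that BOR and PFS exclude, and can give a DOR longer than the same participant's PFS. With the assumed dates and an SFU scan at about Day 143, DOR is 87 days instead of 57. It is larger only if a later assessment, death or last contact sets the end, and is unchanged in the main analysis if there is no later scan and no death. The dates are assumptions. How often this will happen cannot be derived from the SAPs, but few responders are likely to be affected. The text should be corrected before database lock. It does not threaten the primary safety objective.

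**What to change.** In Section 10.1.1 of both SAPs, extend the PFS rule to main and sensitivity DOR: a responder who starts subsequent anti-cancer therapy without prior objective progression is censored at the last tumor assessment before that therapy. State that this takes precedence over the rule censoring deaths without progression at the date of death, and over last-contact censoring in the sensitivity analysis. Carry over the same-day exception. Since BOR accepts a scan on the day new therapy starts, the DOR wording should allow that scan too; otherwise an unconfirmed response first seen that day would be censored before it began. Align the Derivation of Efficacy Endpoints document.

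The cost is SAP wording and reuse of the new-therapy date already derived for PFS; no new data are needed. The downside is that some responders will have a shorter, censored DOR.
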